6. STUDY CALENDAR

Table 2. Study Procedures and assessments

Study Procedures	Registration	Baseline ²	During the Intervention ⁸	Off-intervention ⁹	Survival Follow-up
Informed Consent	X				
Demographics¹		X			
Medical History³		X			
Adherence to clinical care⁴			Continuously throughout the study from Randomization to Off-intervention every 3 months¹¹		
Acute Care Utilization⁵					
Collection of subject's hospital admission and discharge dates⁶					
Survival assessment			X¹⁰		
Subject satisfaction survey			X ⁷	X ⁷	

Key to Footnotes

¹ Demographic information will include: DOB, sex, race, live-in caregiver status, income, insurance status, education level, zip code.

² Screening window is at most 28 days prior to enrollment.

³ The following baseline medical history information will be manually collected from EMR: smoker status, diabetes, ETOH use, BMI, weight, clinically significant pre-existing conditions, and treatment and procedure history.

⁴ Collect the number of visits scheduled for the subject and the number of no-shows, to include all visits scheduled within Atrium Health, not just oncology related.

⁵ Collect unplanned inpatient hospital admissions, emergency room encounters, and urgent care visits.

⁶ Hospitalization encounter is temporally defined as a difference between date of discharge and subtracted date of admission.

⁷ Assessed by a EORTC IL109 customized questionnaire ([Appendix B](#)). It will be collected in two time points. 1st survey will be collected at 4 weeks +2 weeks after the randomization, 2nd survey at 10-14 weeks from the randomization. Subjects will be offered the option to provide survey responses electronically or during a clinic visit. If subject is not able to complete a survey during the study window, they will be asked to complete at the next scheduled in-person visit. This will NOT be considered as a protocol deviation.

⁸ If subject remains on study after the relocation from one LCI site to another LCI site, subject will remain on their original arm he/she was randomized to.

⁹ Subject will become off-intervention and enter the survival follow-up after meeting the criteria for off-intervention, [Section 8.1](#).

¹⁰ Survival will be continuously assessed for subjects who are On Intervention (at least every 3 months \pm 2 weeks). For subjects who are Off Intervention, best effort will be made to obtain survival information approximately every 6 months \pm 4 weeks either by phone or during a clinic visit until the off-study criteria are met ([Section 8.2](#)).

¹¹ Research designee will contact the subject by phone every 3 months \pm 2 weeks, or during a clinic visit.

7. DETAILS ON STUDY ASSESSMENTS

Please also refer to the Study Calendar (Table 2 in Section 6.)

7.1 Screening procedures

Prior to enrollment, subjects will undergo standard screening procedures to confirm whether the subject meets eligibility criteria:

- **Informed Consent:** No protocol-related assessments may be performed prior to obtaining informed consent.
- **Medical History:** A complete relevant medical history should be obtained, including: smoker status, diabetes, ETOH use, BMI, weight, clinically significant pre-existing conditions, and treatment and procedure history.
- **Subject demographics** (DOB, sex, race, live-in caregiver status, income, insurance status, education, zip code) should be recorded.

7.2 During the Intervention

- **Subject satisfaction survey:** a EORTC IL109 customized questionnaire ([Appendix B](#)) will be collected at two time points.
1st survey at 4 weeks +2 weeks after the randomization,
2nd survey at 10-14 weeks from randomization. Patients will be provided with the option to provide survey responses electronically or during a clinic visit.

The following assessments will be performed throughout the study from the Randomization to Off-intervention every 3 months:

- **Acute Care Utilization:** unplanned inpatient admissions, emergency room encounters, and urgent care visits should be collected continuously throughout the study from the randomization.
Hospital admission and discharge dates should be tracked.
- **Adherence to clinical care:** Collect the number of visits scheduled for the subject and the number of no-shows, to include all visits scheduled within Atrium Health, not just oncology related, continuously throughout the study from the randomization.
- **Survival assessment:** Subjects will be assessed during the ONN services continuously throughout the study from the randomization.

7.3 Survival Follow-up

- **Survival assessment:** The best effort will be made to obtain survival information after the subject comes off-intervention until the off-study criteria are met (Section 8.2).

8. OFF INTERVENTION AND OFF STUDY

8.1 Off Intervention

Subjects will be removed from Intervention Status when at least one of the following criteria are met:

- Subject on either arm who permanently discontinues all active anti-cancer therapy
- Subject on either arm who relocates to a non-LCI institution
- Subject on either arm who relocates to an LCI site without LPNP
- Subjects randomized to the ONN arm withdraws consent to participate in the LPNP

8.2 Off Study

Subjects may stop their participation in this study at any time if they no longer wish to participate, or if the investigator believes this to be in the best interest of the subject.

When subjects are removed from the study, the reason for study removal and date the subject was removed should be documented.

Subjects will remain on study until the criteria for final analysis have been met ([Section 11.5](#)).

Reasons a subject may be removed from study prior to meeting the criteria for final analysis include, but are not limited to:

- The subject or legal representative (such as a parent or legal guardian) withdraws study consent or study participation
- Study is terminated early ([Section 12](#))
- Investigator's decision to withdraw the subject
- Subject death

Subjects that are Off Study will not participate in any study related procedures, including data collection. The completion of this study is not related to the continuance of cancer care.

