5.4 Duration of Data Acquisition

Underlying primary data needed to support study endpoints will be acquired by trained study conduct research staff. For each subject, this will be done starting at the day of randomization and then on an every 3-month basis.

The duration of data acquisition will be as follows:

- For ACU, readmissions, adherence to clinical care, and subject satisfaction, the duration of data acquisition will be until the subject meets the criteria for off-intervention (see Section 8.1)
- For survival data, the duration of data acquisition will be until the subject becomes off study (see Section 8.2).

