8.3 Special Considerations

Subject Relocation: At any point during the conduct of the trial, the subject may desire to relocate from their present LCI study site to another LCI facility with LPNP due to travel feasibility or other circumstances. If subject relocates away from the study site, the present study site Sub-Investigator will consult with relocation-site Sub-Investigator to determine if subject should continue study participation. If subject remains on study, subject will remain on their original arm he/she was randomized to.

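### Off-study status ends survival collection even where consent stands, and Sections 8.2 and 8.3 let investigators impose it without criteria

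*Combined protocol and SAP*

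**What the plan says.** All references are to the combined protocol and SAP.

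- **Effect of off-study status.** Section 8.2: "Subjects that are Off Study will not participate in any study related procedures, including data collection". Section 5.4 agrees: "For survival data, the duration of data acquisition will be until the subject becomes off study". Section 7.3 sets the same end point for survival follow-up after the intervention.
- **Who can impose it.** Section 8.2 lets participation stop if the subject wishes, "or if the investigator believes this to be in the best interest of the subject". Its list of removal reasons contains "Investigator's decision to withdraw the subject", gives no criteria for that decision, and is open-ended ("include, but are not limited to").
- **Moves within LCI.** Section 8.3 concerns a subject moving to another LCI facility that has LPNP. The present Sub-Investigator "will consult with relocation-site Sub-Investigator to determine if subject should continue study participation". Calendar footnote 8 gives the rule for a subject who stays on study after such a move, so not staying is contemplated.
- **Other moves.** Section 8.1 lists "Subject on either arm who relocates to a non-LCI institution", and also a move to an LCI site without LPNP, as reasons for going off intervention only. Calendar footnote 9: "Subject will become off-intervention and enter the survival follow-up after meeting the criteria for off-intervention".
- **Use of the data.** Section 11.3.1 defines OS6 as vital status six months after randomization. Section 11.4 bases all primary and secondary analyses on evaluable subjects, who must have died within six months or been on study at least that long. Section 11.3.2 censors OS at the date last known alive.

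**The concern.** The plan has two exits. Off-intervention ends navigation and keeps survival follow-up. Off-study ends both. The second can be used for a subject who has withdrawn nothing, on a judgement for which no criteria are written.

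The relocation rules also point in opposite directions. A subject who leaves LCI stays in survival follow-up. One who moves to another LCI site with navigation may be removed from the study altogether.

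What is at stake is a co-primary endpoint. Removal happens after randomization, and those deciding are not described as blinded to arm. The only blinding mentioned is that of the interim efficacy analyses in Section 11.5.8. If removal tracks decline and differs between arms, the OS6 comparison is made on a selected group and the OS censoring is informative.

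**Working it through.** **Step 1: the rules side by side**

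| Event, consent not withdrawn | Section | Status | Survival follow-up |
|---|---|---|---|
| Moves to a non-LCI institution | 8.1, footnote 9 | Off intervention | Continues |
| Moves to an LCI site without LPNP | 8.1, footnote 9 | Off intervention | Continues |
| Moves to an LCI site with LPNP | 8.3 | Sub-Investigators decide | Ends if they decide against continuing |
| Investigator's decision | 8.2 | Off study | Ends |

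The Section 8.3 sentence on the consultation speaks only of relocating away from the study site. Read broadly, it would also cover the first two rows and contradict Section 8.1 outright. Read narrowly, it leaves the reversal shown in the table. The passages need reconciling on either reading.

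**Step 2: what happens to a subject removed alive at, say, month 3**

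- OS6: the subject has not been on study for six months. A death before month 6 would qualify the subject as evaluable if it were known, but collection has stopped and no route for learning of it is given.
- OS: time up to removal is kept and censored at the last known alive date. The Kaplan-Meier 12-month estimate in Section 11.5.5 uses that time.
- A subject removed after month 6 still counts for OS6.

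**Step 3: how large the effect could be**

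The plan gives no figure for this route, so there is none to reproduce. What follows is a sensitivity range.

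Inputs from the plan: control OS6 of about 60%, 150 evaluable subjects per arm, and two-sided alpha of 0.025 for each co-primary endpoint (Sections 11.2 and 11.5.8).

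Assumptions, not in the plan: true OS6 is 60% in both arms, and a share r of one arm is removed alive before month 6, with true OS6 of q among those removed.

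Observed OS6 in the affected arm is S = (0.60 − r·q)/(1 − r), on n = 150(1 − r) subjects. The other arm stays at 0.60 on 150. The rejection probability is that of a pooled two-proportion z-test with critical value 2.241:

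Φ((d − 2.241·SE0)/SE1) + Φ((−d − 2.241·SE0)/SE1), where d = S − 0.60, SE0 is the pooled standard error and SE1 the unpooled one.

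Worked case, r = 10% and q = 20%:

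- S = (0.60 − 0.02)/0.90 = 0.644 on n = 135, so d = 0.0444.
- Pooled rate = (90 + 87)/285 = 0.621.
- SE0 = √(0.621 × 0.379 × (1/150 + 1/135)) = 0.0576.
- SE1 = √(0.24/150 + 0.644 × 0.356/135) = 0.0574.
- Type I error = Φ(−1.47) + Φ(−3.02) = 0.072.

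| Share removed, r (of 150) | Observed OS6, q = 40% to 20% | Two-sided type I error, q = 40% / 30% / 20% |
|---|---|---|
| 2% (3 subjects) | 60.4% to 60.8% | 0.025 / 0.026 / 0.027 |
| 5% (7.5) | 61.1% to 62.1% | 0.027 / 0.031 / 0.035 |
| 10% (15) | 62.2% to 64.4% | 0.036 / 0.050 / 0.072 |

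Two checks on the formula. If those removed have the same prognosis as everyone else (q = 60%), S = 0.60 and there is no bias. If the same r and q apply in both arms, both observed rates shift equally and the null comparison is unaffected. The bias needs removals that are both prognostic and unequal between arms.

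**The case against.** The strongest reply is that investigator discretion is ordinary wording and may never be used. Section 8.3 prescribes a consultation, not removal. Section 8.2 requires the reason and date of removal to be recorded, Section 9 has the sponsor team review retention and report to the monitoring committee, and Section 11.5.2 puts discontinuations and their reasons in the CONSORT summary. Nothing in the documents suggests that removals would favour one arm. All of this stands, and it limits the size of the point. These safeguards would make selective removal visible, but they would not recover the missing vital status.

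Enrolment also continues until 300 subjects are evaluable. That restores the count but not the selection: S above does not depend on n.

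A reader might infer several stronger things that the documents do not support:

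- **That the 47 enrolled but non-evaluable subjects (347 − 300, or 13.5% of 347) measure this loss.** That allowance covers all causes, including subjects who receive no systemic therapy on or after enrollment and those who withdraw consent. The share due to investigator removal could be zero.
- **That one or two removals could turn a near miss into a significant result.** This depends on a test variant that Section 11.5.4 does not name, on a result chosen to lie near the threshold, and on every removal falling in one arm.
- **That subjects who leave LCI are followed until they die.** Calendar footnote 10 promises best-effort contact about every six months until the off-study criteria are met, and Section 8.2 ties that end to the final analysis.
- **That removal erases a subject's survival data altogether.** Time before removal is kept for OS, and an analysis of all randomized subjects would use it. Only vital status after removal is missing.

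**Conclusion.** The point holds as a gap in the follow-up rules. Sections 5.4, 7.3 and 8.2 together stop survival collection for subjects who may not have withdrawn consent, on a decision without criteria, and Section 8.3 sits awkwardly with Section 8.1 and calendar footnote 9.

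The size of the effect is unknown and may be small. It is negligible at 2% removal from one arm. At 5% to 10% the two-sided type I error is about 0.027-0.072 against 0.025, provided that removals fall in one arm and that those removed have a true OS6 of 20-40% against 60% overall. Neither condition is stated or implied by the documents. The case for acting rests mainly on the low cost of the change and on the endpoint being co-primary. There is no evidence that bias has occurred.

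No benefit from stopping vital-status collection is apparent where consent stands. The synopsis and Section 5 say that enrolment does not alter cancer treatment, and off-intervention status already allows navigation to end.

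**What to change.** - **Section 8.2:** state that a subject removed by investigator decision, who has not withdrawn consent to data collection, stays in vital-status follow-up from records, or by phone where acceptable, until death, withdrawal of that consent, or study end. Align Sections 5.4 and 7.3.
- **Section 8.3:** limit the Sub-Investigators' relocation decision to intervention status, so that survival follow-up continues after a move between LCI sites, and reconcile the wording with Section 8.1 and calendar footnotes 8 and 9.

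The investigator can still end a subject's other participation. The cost is a wording amendment, possibly one sentence in the consent form, and a few extra record or phone checks. No sample-size figure changes.

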8.3 Special Considerations

Subject Relocation: At any point during the conduct of the trial, the subject may desire to relocate from their present LCI study site to another LCI facility with LPNP due to travel feasibility or other circumstances. If subject relocates away from the study site, the present study site Sub-Investigator will consult with relocation-site Sub-Investigator to determine if subject should continue study participation. If subject remains on study, subject will remain on their original arm he/she was randomized to.

9. DATA AND SAFETY MONITORING PLANS

Data will be collected in electronic case report forms (eCRFs). The database uses fully validated secure web-enabled software that conforms with 21CFR Part 11 requirements. Study personnel will be trained on data entry by the sponsor and provided protocol-specific eCRF guidelines.

This protocol will be monitored according to the processes in effect for all LCI investigator-initiated studies and the protocol-specific monitoring plan, the protocol-specific Data Management Plan (DMP).

and will abide by applicable regulations and guidelines (e.g. Good Clinical Practice [GCP]). It is the responsibility of the Sponsor-Investigator to monitor the studysafety data for this study. The Sponsor-Investigator and other sponsor-level team members will meet regularly to monitor subject consents, enrollment and retention, studyafety data, and timeliness/validity/integrity of the data. Documentation of these meetings will be kept with study records. The Sponsor-Investigator will submit reports to the LCI Data and Safety Monitoring Committee according to the institutional Data and Safety Monitoring Plan.

This study will be monitored to ensure the study is conducted in compliance with the study protocol, SOPs of the LCI and Atrium Health Office of Clinical and Translational Research (and/or other participating institutional SOPs), the FDA, and other applicable regulations and guidelines (e.g. GCP).

Investigators and/or their delegated study personnel will be required to be available during the monitoring visits.

10. POTENTIAL RISKS/UNANTICIPATED PROBLEMS

10.1 Potential Risks

10.1.1 Subject Confidentiality

We do not anticipate any breach of confidentiality as no records will be shared with any personnel outside the research team. All medical information including assessments and other medical records will be recorded and stored in a database. The database will exist on a password protected secured server. Medical records data will be abstracted by the Research Designee. All records will be kept confidential.

~~All data and records generated during this study will be kept confidential in accordance with Institutional policies on subject privacy and HIPAA; the investigators and other site personnel will not use such data and records for any purpose other than conducting the study. No breach of confidentiality is anticipated because no records will be shared with any personnel outside the research team. All medical information including assessments and other medical records will be recorded and stored in a database. The database will exist on a password protected secured server. All records will be kept confidential.~~

~~To minimize risks to confidentiality, data will only be monitored by Sponsor Investigator and trained research staff. At a minimum, research staff will have completed basic human subject protection research training.~~

10.1.2 Emotional Distress

Some questions in the questionnaires could create emotional distress or confusion. If a subject experiences distress or confusion, the questionnaire process will be interrupted or discontinued, and the Research Designee will follow up with the Sponsor-Investigator.

10.2 Unanticipated Problems (UAP)

10.2.1 Definition

A UAP is any incidence, experience or outcome that is unexpected (e.g., a lost or stolen laptop computer that contains sensitive study information) given the information provided in research-related documentation (e.g., informed consent) and the study population characteristics, that is related or possibly related to participation in the research study and places the participant at an increased risk.

10.2.2 Reporting

All UAPs occurring during the conduct of a protocol and meeting the definition of a UAP will be reported to the Sponsor-Investigator and IRB per IRB reporting requirements.

11. STATISTICAL CONSIDERATIONS

11.1 Milestones

11.1.1 Registration Date

The date the subject signs the informed consent.

11.1.2 Enrollment Date

The date that the subject is randomized.

11.1.3 Intervention Discontinuation Date

The date when S-I becomes aware of the subject meeting any of the criteria in Section 8.1.

11.1.4 Off Study Date

The date the subject terminates participation on the study or is removed from the study per the criteria in Section 8.2.

11.2 Sample Size

This study is designed with co-primary objectives to evaluate the acute care utilization and 6-month OS rate. Power and sample size calculations were primarily calculated based on the OS landmark objective. The overall type I error rate for this study is alpha = 0.05. Therefore, the co-primary endpoints were both powered at the 2-sided alpha = 0.025 significance level. We estimate that treatment with standard therapy results in median survival of 8 months. Assuming an exponential distribution, this corresponds to a 6-month survival rate of approximately 60%. Therefore, the primary OS objective of this study is designed to test the null hypothesis that the 6-month OS survival rate is \leq 60%. A total of 300 evaluable subjects enrolled in a one-to-one fashion will provide 80% power, assuming the true 6-month OS rate with Nurse Navigation is 80%. A total of 347 subjects may need to be enrolled to achieve 300 evaluable subjects. A 20% improvement in the 6-month OS rate is considered clinically relevant. This sample size will also provide at least 93% power to detect a 20% reduction in acute care visits (assuming there will be 6 acute care utilization visits per year in the control arm).

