11.5 Analysis Methods

11.5.1 Timing of Analysis

An interim analysis will occur after 100 subjects have been enrolled in the evaluable population. A second interim analysis will occur after 85 deaths have occurred in the evaluable population. A third interim analysis will occur after 120 deaths have occurred in the evaluable population. Analyses of the primary objectives will occur after 300 subjects have been enrolled in the evaluable population. A final analysis will occur when the OS censoring rate reduces to 20% or when all surviving subjects (who remain on study) are on study for at least 30 months (whichever occurs first).

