11.5.4 Primary Analysis

The frequency and proportion of subjects alive at 6 months or better will be calculated for each study arm. Corresponding 95% confidence intervals will be estimated using the Clopper-Pearson method. A

two-sided test for binomial proportions will be carried out, testing the null hypothesis that there is no difference in the OS6 rate between the arms.

Poisson regression analyses will be used to analyze acute care utilization visits. Treatment arm will be included in the model as the primary covariate and an asymptotic test of significance will be carried out to compare acute care utilization between the arms.

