11.5.8 Interim Analysis

After 100 subjects have been enrolled in the OS evaluable population, a formal interim analysis will be conducted. The interim analysis is designed primarily to assess futility regarding the 6-month OS rate objective and will be based on the conditional power. If the conditional power falls below 50%, the OS6 objective may be removed from the co-primary objective. If this occurs, the primary objective will be based only on the acute care utilization objective. With this revised design, 158 evaluable subjects would provide 90% power to detect a 20% reduction in acute care utilization from 6 visits per year in the non-navigation arm based on a 2-sided alpha = 0.05 significance level.

If the OS6 conditional power is greater than 50% but less than 80%, the sample size may be increased so that the power for the revised sample size is maintained at 80%. As discussed in Chen et al, 2004, this sample size re-estimation will not inflate the type I error.

Sample size re-estimation

As per protocol, the interim futility analysis occurred on 9/22/2022. Based on the results of the interim analysis and on the initial statistical design, the trial will proceed with OS6 and ACU as co-primary

endpoints. In order to retain 80% power for the OS6 objective, the sample size will be increased from 107 evaluable subjects per arm to 150 evaluable subjects per arm.

In order to achieve a total of 300 evaluable subjects, it is estimated that approximately a total of 347 subjects may be enrolled.

Additionally, ~~an~~ interim efficacy analysisanalyses will be performed after 85 and 120 deaths in the evaluable population have occurred (Interim Efficacy Analysis I and II). This will be conducted under the auspices of the LCI DSMC and will be blinded to the Sponsor-Investigator and the study conduct trial site. If, in the clinical judgement of the LCI DSMC, there are impelling favorable OS trends, the study may be terminated due to ethical considerations. No formal statistical stopping rules will be utilized, and no alpha spend will be incurred due to this interim efficacy evaluation.

As per protocol, Interim Efficacy Analysis I occurred on 1/23/2022. Based on the results of the blinded survival analysis and the updated statistical design (following the interim futility analysis on 9/22/2022), the trial will continue and Interim Efficacy Analysis II will be performed after 120 deaths in the evaluable population have occurred.

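### The equal 0.025/0.025 split of alpha between OS6 and acute care utilization is valid, but Holm's procedure would give each endpoint more power at the same overall 0.05

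*Combined protocol and SAP*

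**What the plan says.** Section 11.2 states "The overall type I error rate for this study is alpha = 0.05" and from this concludes that "the co-primary endpoints were both powered at the 2-sided alpha = 0.025 significance level". The Synopsis repeats it. That is an equal Bonferroni allocation.

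Section 11.5.1 sets one time for both primaries: "Analyses of the primary objectives will occur after 300 subjects have been enrolled in the evaluable population".

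Section 11.5.4 gives one test per endpoint. OS6 has a two-sided test of two proportions, "testing the null hypothesis that there is no difference in the OS6 rate between the arms". ACU has a Poisson regression with an asymptotic test of the arm effect. The section states no significance level, no testing order and no rule for carrying alpha from one endpoint to the other.

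The only reallocation of alpha is in Section 11.5.8: ACU would be tested at 0.05 if OS6 were dropped at the futility look. That did not happen. The trial continues with both endpoints, and "the sample size will be increased from 107 evaluable subjects per arm to 150 evaluable subjects per arm" to keep 80% power for OS6.

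**The concern.** Deriving 0.025 for each endpoint from an overall 0.05 implies that a win on either endpoint counts. If both had to succeed, no split would be needed. Once one endpoint is significant at 0.025, its share of alpha can be passed to the other without raising the family-wise error. A plain split does not use it, so a second endpoint with p between 0.025 and 0.05 would be missed.

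This matters because the stated hypothesis covers both utilization and survival, and because 86 evaluable subjects (300 − 2 × 107) were added to protect OS6 power. Holm would add some power to each endpoint without enrolling anyone.

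**Working it through.** **Inputs from the documents.** Overall alpha 0.05, with 0.025 two-sided per endpoint (11.2). OS6 60% versus 80%, 150 per arm, stated power 80% (11.2). ACU 6 visits per year in control and a 20% reduction, so 4.8; stated power at least 93% (11.2). Earlier size 107 per arm; ACU-only fallback of 158 subjects with 90% power at 0.05 (11.5.8).

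**Assumed, because the plan gives no value.** Exposure per subject, overdispersion, independence of the two tests and, in case C, 76% OS6 with navigation.

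**Formulas.** Critical values are z = 2.2414 at 0.025 and 1.9600 at 0.05.
- OS6 power = Φ{[d − z·√(2p̄(1−p̄)/n)] / √([p₁(1−p₁)+p₂(1−p₂)]/n)}.
- ACU power = Φ{ln(6/4.8)/SE − z}, with SE = √{φ[1/(6nt) + 1/(4.8nt)]}, t = years of exposure, φ = dispersion.

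**The plan's own figures.**
- Alpha: 0.025 + 0.025 = 0.05, as stated.
- ACU, t = 1, φ = 1: 93.7% at 107 per arm and alpha 0.025; 90.0% at 79 per arm and alpha 0.05. Both stated ACU figures are therefore consistent with one year of exposure. At 150 per arm the power is 98.7%, which agrees with at least 93%.
- OS6 at 150 per arm: (0.20 − 2.2414 × 0.05292)/0.05164 = 1.576, so 94.3% (92.6% with continuity correction), not 80%. The 80% fits 107 per arm (83.5% without correction, 79.4% with it). That mismatch is a separate matter, so both starting points are used below.

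**Holm for two tests.** Reject an endpoint if its p ≤ 0.025, or if its p ≤ 0.05 and the other p ≤ 0.025. Write O and A for the powers of OS6 and ACU at 0.025, and O′ and A′ for those at 0.05. Under independence:
- OS6: O + A(O′ − O)
- ACU: A + O(A′ − A)
- Both: OA′ + AO′ − OA, against OA for the split
- At least one: 1 − (1−O)(1−A), the same for either procedure

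**Case A, stated powers.** O = 0.80 gives O′ = Φ(0.8416 + 2.2414 − 1.9600) = 0.8693. A = 0.93 gives A′ = Φ(1.4758 + 0.2814) = 0.9606. Holm OS6 = 0.80 + 0.93 × 0.0693 = 0.8644.

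**Case B, 60% versus 80%, 150 per arm, t = 1, φ = 1.** O = 0.9425 and O′ = Φ[(0.20 − 1.9600 × 0.05292)/0.05164] = 0.9689. SE = √(1/900 + 1/720) = 0.05, so A = Φ(4.463 − 2.241) = 0.9868 and A′ = 0.9938.

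**Case C, 60% versus 76%, 150 per arm, t = 0.75, φ = 2 (all but 60% and 150 assumed).** O = Φ[(0.16 − 2.2414 × 0.05386)/0.05307] = 0.770 and O′ = 0.847. SE = √[2(1/675 + 1/540)] = 0.0816, so A = 0.688 and A′ = 0.780.

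| Case | OS6, split → Holm | ACU, split → Holm | Both, split → Holm | At least one |
|---|---|---|---|---|
| A | 80.0 → 86.4% | 93.0 → 95.4% | 74.4 → 83.3% | 98.6% |
| B | 94.3 → 96.9% | 98.7 → 99.3% | 93.0 → 96.3% | 99.9% |
| C | 77.0 → 82.3% | 68.8 → 75.9% | 53.0 → 65.4% | 92.8% |

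**Range around C, 76% held.** With t = 1 and φ = 1, OS6 rises to 84.6% and both from 76.0% to 84.2%. With t = 0.5 and φ = 2 (SE = 0.10, A = 0.496, A′ = 0.607), OS6 rises to 80.9% and both from 38.2% to 50.6%.

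**Dependence.** Death shortens the time in which visits can occur, so exact independence is unlikely. Simulating case A with a correlation of 0.5 between the test statistics gives OS6 86.1%, ACU 94.6% and both 76.9% → 84.5%. The gain is not an artefact of independence.

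**Error control.** If both nulls are true, Holm makes a false rejection only when the smaller p ≤ 0.025, with probability at most 0.05 (0.0494 under independence). If one null is true, a false rejection needs that p ≤ 0.05. Neither step uses an assumption about dependence.

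**The case against.** **The split is legitimate.** It controls 0.05, the trial was sized on it, and nothing in the documents contradicts it. This stands. A reader might infer a multiplicity error, but the documents do not support that.

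**The plan does not say each endpoint stays at 0.025 after the other succeeds.** This also stands. Section 11.2 speaks of powering, and 11.5.4 states no threshold. What can be said is that no rule for passing alpha is written. A decision rule needs to be written in any case.

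**The larger gains rest on outside inputs.** This is right for case C: 76%, nine months and dispersion 2 do not come from the plan. At its planning effects and an assumed one year of exposure, OS6 gains only about 2.6 points.

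**Either-endpoint success is no more likely.** True: Holm leaves the chance of at least one win unchanged. A reader who takes the power gains as a better chance of a positive trial would be mistaken.

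**Holm needs a valid ACU p-value.** True, and so does the split. Section 11.5.4 names Poisson regression with no dispersion adjustment. With true dispersion 2, an unscaled test at nominal 0.025 has actual error 2[1 − Φ(2.2414/√2)] = 11.3%, and at nominal 0.05 it has 16.6%. Allowing ACU 0.05 after an OS6 win makes the adjustment more important.

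**It would be a change after interim looks.** The futility look has changed the sample size. Section 11.5.8 states blinding of the Sponsor-Investigator for the efficacy looks only. The change therefore needs an amendment and a record that results by arm were not known. It does not disturb the re-estimation argument: conditional power above 50% at the 0.025 critical value is also above 50% at the 0.05 critical value.

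**Conclusion.** A cheap improvement, not an error. With both primaries analysed at one time, Holm rejects everything the equal split rejects at the same family-wise 0.05. Under independence, OS6 gains 6.4 points from the stated 80% and about 2.6 points at 60% versus 80% with 150 per arm. Power for both gains 8.9 points (74.4% to 83.3%) and 3.3 points (93.0% to 96.3%) respectively. The gain is larger if the effect is smaller or ACU information is thinner than planned, but that rests on assumed inputs. The conclusion that Holm is never worse needs no assumption about dependence. It does need a valid ACU test and the either-endpoint reading of success.

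**What to change.** In Sections 11.2 and 11.5.4, state that the two primary hypotheses are tested by Holm's procedure at overall two-sided 0.05: the smaller p-value against 0.025 and, if that is rejected, the other against 0.05. Specify that the ACU p-value comes from a method valid under overdispersion, such as a scaled or robust variance or a negative binomial model. Adopt this by amendment before the primary analysis, and document that it was made without knowledge of interim results by arm.

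Cost: an amendment and a short addition to two sections, with no further subjects and no added family-wise error given a valid ACU test. Simultaneous confidence intervals become slightly less simple to report.
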